2.3.2 Protocol Deviations

Subjects with deviations will be summarized and listed individually. Summaries will be by COVID-19 related deviations and overall. Listings will include subject number and observed deviation.

2.3.3 Demographic Characteristics

Age, body mass index (BMI) and [REDACTED] will be summarized as continuous variables. Gender, race, ethnicity, Fitzpatrick skin type, and childbearing potential will be summarized as categorical variables.

2.3.4 Medical History, Medications, and Procedures

Medical history and cosmetic history were captured in the pivotal study, and will be summarized for the Extension population.

Concomitant medications will be coded using the World Health Organization Drug Dictionary (WHODD). Concomitant procedures/non-pharmacological treatments will be coded according to Medical Dictionary for Regulatory Activities (MedDRA).

Concomitant therapies are defined as follows:

- Any therapy ongoing at the time of V11/Week 48.
- Any changes to existing therapies (such as changes in dose or formulation) during the course of the study, or
- Any new therapies started after V11/Week 48.

Subjects reporting concomitant medications will be summarized separately, by WHODD Anatomical Therapeutic Chemical (ATC) Class Level 3 (if Level 3 is not available, the highest class available will be used) and WHODD generic name. Additionally, concomitant medications taken due to adverse events will be summarized separately.

Prior and concomitant procedures will be listed.

2.4 Effectiveness Analysis

2.4.1 Datasets Analyzed

All effectiveness variables will be analyzed based on the Extension population.

2.4.2 Handling of Missing Data

The number of missing values will be summarized and reported as appropriate.

All effectiveness endpoints will be evaluated based on Observed Cases.

2.4.3 Effectiveness Analysis

The baseline value is defined as the observation that is closest to but prior to study treatment at the baseline visit/first treatment in the 43USSA1705 study. Change from baseline is calculated as the value minus the baseline value.

Exact confidence intervals will be used for the proportions, i.e. they will be based on the binomial distribution. For the presentation of effectiveness data, all time points from baseline throughout the study will be presented for the Extension population.

The change from baseline in [REDACTED] at each follow-up visit based on the Evaluator's assessment, for the right and left side of the face separately, will be calculated using descriptive statistics. In addition, the number and percent of subjects in each response category will be presented. The

[REDACTED] be calculated along with their two-sided exact 95% confidence interval.

The proportion of improved subjects based on [REDACTED] at each follow-up visit will be calculated along with their two-sided exact 95% confidence intervals. The proportions will be calculated separately for the subject's assessment and for the Investigator's assessment. [REDACTED]

[REDACTED] In addition, the number and percent of subjects in each response category will be presented.

[REDACTED] lds

[REDACTED] scores will calculated and presented at all follow-up visits using descriptive statistics. The number and percent of subjects in each response category for each question will also be presented.

Subject satisfaction

Subject satisfaction will be presented using descriptive statistics as appropriate for each follow-up visit.

2.5 Safety Analysis

Safety endpoints will be summarized using descriptive statistics using the Observed Cases. There are no planned inferential statistical analyses of safety endpoints.

2.5.1 Adverse Events

All AEs will be coded according to MedDRA and summarized by system organ class (SOC) and preferred term (PT).

A summary of all AEs (number and percentage of subjects with at least one event and number of events) will be provided, which will include:

- Subjects with at least one AE (in total as well as serious AEs).
- Subjects with at least one study product or injection procedure-related AE (in total as well as serious AEs).
- Subjects with at least one unrelated AE (in total as well as serious AEs).
- Number of subjects who did not have an AE.

Statistical Analysis Plan, Version 1.0 FINAL, 10 AUG 2020

The number of subjects with AEs related to study product or injection procedure as well as the number of events will be summarized by SOC, PT, and severity.

In addition, for related AEs the number of days to onset from last treatment (in the 43USSA1705 study) and the duration of event will be summarized by SOC and PT using mean, SD, min, max and median.

- Time to onset of an AE will be derived as the start date minus the date of the most recent treatment. If the start date is missing, it will be assumed that the AE started on the first day of the extension study.
- Duration of an AE will be derived as the stop date minus the start date + 1. Missing stop dates will not be imputed and therefore no duration will be calculated in these cases.

Action taken for related AEs will also be summarized. Non-related AEs will be summarized by SOC, PT, and intensity.

These summaries will be performed for:

- The whole period from baseline [REDACTED] to the end of the extension study [REDACTED]
- The period from baseline to the end of the 43USSA1705 study ([REDACTED])
- The period from start of the extension study [REDACTED] to the end of the extension study [REDACTED]

Serious AEs that starts during the extension study will be listed.

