5.5 Withdrawal of subjects

Each subject shall be advised in the informed consent form that the subject has the right to withdraw from the study at any time, for any reason, without prejudice. Subjects may also be discontinued from Page 19 of 37

this study if the Investigator determines that it is in the subject's best interest to do so and may be withdrawn at the Investigator's discretion at any time.

The withdrawal criteria are:

The reason and date for withdrawal shall be documented in the eCRF. When possible, an explanatory comment shall be added to further explain the reason for withdrawal. If withdrawal of a subject occurs during a regular study visit, the eCRF for that specific visit shall be completed as far as possible.

If a subject is withdrawn from the study, all data collected until the time of withdrawal will be used in the analyses. Subjects who are withdrawn or discontinued from the study will not be replaced. For AEs still ongoing at the time of withdrawal, see section 7.2.6.

Study Products

No study products will be provided during this study.

6.1 **Investigational product**

No investigational product will be provided during this study.

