7.2.3.2 Causal relationship and seriousness

Reporting of adverse events

Adverse event reporting on each subject shall start upon enrollment (singing of the informed consent) in the study.

The reporting shall continue during each follow-up visit (including any telephone contacts and extra visits between planned visits) until the last scheduled visit in the study.

[figure not shown]
All AEs, non-serious as well as serious, are to be reported as an AE in the eCRF.

Reporting of serious adverse events

The Investigator shall report any SAE to the Contract Research Organization (CRO) immediately but not later than 24 hours of awareness of the event. This initial report can be made via e-mail or submitted via the eCRF.

In case of difficulty to obtain all the required information within 24 hours, an initial report can be submitted, with the following information as a minimum, irrespective of whether some of it is regarded as preliminary:

Follow-up information and data missing in the initial SAE reporting shall be gathered as soon as possible and reported to the CRO immediately but not later than 24 hours of awareness of the new data. Complete and adequate information on each SAE is required. All attempts to obtain this information, including dates for follow-up activities, must be documented by the Investigator or designated study staff.

Supporting documentation to be provided with the SAE report:

- Concomitant therapies form/list
- AE form/list
- Medical history form/list
- Study treatment CRF form
- Any other relevant supporting documentation (e.g. hospital notes, death certificate, autopsy reports etc.)

E-mail for SAE reporting:		

The SAE form must be signed and dated by the Investigator. If the initial 24-hour SAE report does not contain full information or if it is made without using the SAE form the fully completed and signed SAE form shall be e-mailed as noted above. A copy of the fully completed SAE form shall be kept at the site.

In addition, the Investigator shall report SAEs to the responsible IRB without undue delay. The Investigator is responsible for checking what reporting procedures are applicable for his/her IRB regarding SAEs and final report of the outcome of the study and to comply with such reporting procedures during the study period. For non-urgent complementary information not possible to send by e-mail, please use surface mail.

[figure not shown]

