2.2 Analysis Populations

Only one population will be defined: The Extension population. The Extension population includes all subjects entering the extension study. This would include all subjects who are signing the extension study informed consent.

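### AE incidence is planned only as a crude percentage of subjects, which would understate extension-period incidence if follow-up is incomplete

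*SAP*

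**What the plan says.** Incidence is the first-named component of the safety endpoint (Protocol 3.1, SAP 1.6), and long-term safety is the safety objective.

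- **Measure.** SAP 2.5.1 gives the "number and percentage of subjects with at least one event and number of events", overall and by relatedness, together with a row for the "Number of subjects who did not have an AE". Time to onset is summarised only for related events that occurred. No subject-years, exposure-adjusted rate or cumulative incidence is named.
- **Population.** SAP 2.2: "Only one population will be defined: The Extension population". On membership it adds: "This would include all subjects who are signing the extension study informed consent". No minimum follow-up is required.
- **Safety basis.** SAP 2.5: "Safety endpoints will be summarized using descriptive statistics using the Observed Cases". It does not say what an observed case is for a subject-level AE percentage, and it names no denominator. SAP 2.4.1 does name one for effectiveness: "All effectiveness variables will be analyzed based on the Extension population".
- **Collection.** The protocol section on reporting of adverse events: "Adverse event reporting on each subject shall start upon enrollment (singing of the informed consent) in the study". Reporting runs to the last scheduled visit.
- **Withdrawal.** Protocol 5.5 keeps the data gathered up to withdrawal and says: "Subjects who are withdrawn or discontinued from the study will not be replaced".
- **Periods.** SAP 2.5.1 repeats the summaries for the whole period, the pivotal period and the extension period. SAP 1.1.1 has subjects enter on completing the pivotal study.

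**The concern.** A crude percentage estimates 48-week incidence without bias only if everyone in the denominator is observed for 48 weeks. A subject who leaves at week 20 without an event stays in N and is tabulated as having had no AE, although nothing is known about the remaining 28 weeks.

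The plan itself allows for incomplete follow-up. SAP 2.3.1 tabulates missed visits and withdrawals by visit, and SAP 2.3.2 separates COVID-19-related deviations.

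The effect falls on the period the study was set up to describe. Pivotal-period follow-up should be essentially complete in this population, because completing the pivotal study is the route of entry. Extension follow-up may not be. Both periods are nevertheless shown as n/N, so a reader who sets them side by side could take missing observation for a lower event rate. SAP 2.5.2 repeats the crude measure for related events by centre. About 60 subjects at five sites averages 12 per centre, so one subject lost early is about 8% (1/12) of a centre's denominator.

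**Working it through.** **No planned figure to reproduce.** SAP 1.1.2 says no sample size calculation is needed, and neither document states a drop-out or AE rate. The calculation below is illustrative.

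**Inputs from the SAP.** Follow-up of 48 weeks (1.1.1) and N of about 60 (1.1.2).

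**Assumptions.** True 48-week incidence P with constant hazard. A share d of subjects drops out, independently of AE risk, at times uniform over the 48 weeks. Events before drop-out are counted, as Protocol 5.5 provides.

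**Formulae.** With time in units of 48 weeks, the hazard is L = −ln(1 − P). The chance that a drop-out has an event before leaving is the average of 1 − exp(−Lt) over t from 0 to 1:

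p_d = 1 − (1 − exp(−L))/L = 1 − P/L

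Expected crude percentage = (1 − d)·P + d·p_d

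**For P = 20%.** L = 0.2231 and p_d = 1 − 0.20/0.2231 = 0.1037.

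- d = 0: 20.0%
- d = 10%: 0.9 × 0.20 + 0.1 × 0.1037 = 19.0%
- d = 20%: 0.8 × 0.20 + 0.2 × 0.1037 = 18.1%
- d = 30%: 0.7 × 0.20 + 0.3 × 0.1037 = 17.1%

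**Range over P and drop-out timing** (expected crude percentage)

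| True P | Drop-out timing | d = 10% | d = 20% | d = 30% |
|---|---|---|---|---|
| 10% | uniform | 9.5 | 9.0 | 8.5 |
| 10% | all right after consent | 9.0 | 8.0 | 7.0 |
| 20% | uniform | 19.0 | 18.1 | 17.1 |
| 20% | all right after consent | 18.0 | 16.0 | 14.0 |
| 40% | uniform | 38.2 | 36.3 | 34.5 |
| 40% | all right after consent | 36.0 | 32.0 | 28.0 |

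The second row for each P is the extreme case p_d = 0, so the crude figure is (1 − d)·P. Under uniform drop-out the relative shortfall is about 5%, 9–10% and 14–15% at the three drop-out levels.

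**Scale against sampling error.** At P = 20% and N = 60, the expected number of subjects with an event falls by 60 × (0.200 − 0.190) ≈ 0.6, then 1.2 and 1.7, using unrounded values. The exact 95% interval for 12/60 is 10.8% to 32.3%, so the shift is small beside the sampling error. It is nevertheless systematic in direction under these assumptions, and the SAP plans no interval for AE percentages.

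**The case against.** The strongest case against runs as follows.

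1. **A reader might infer that early drop-outs are simply counted as AE-free.** They are not. Reporting starts at consent, and data up to withdrawal are used, so a drop-out with an earlier event counts as a case. In the whole-period table an event in the pivotal study counts too. Only the unobserved later time is treated as event-free. Protocol 7.2.7 also asks for related events with onset after the last visit to be reported if the investigator learns of them. That is passive capture of related events, not follow-up.
2. **A reader might infer that screen failures dilute the denominator.** The documents do not establish this. Exclusion criteria exist beside consent, and no visible rule covers a consented but ineligible subject. But SAP 2.2 also describes the population as those entering the extension, subjects come straight from the pivotal study, and no screen-failure number is given. It may be zero.
3. **The denominator is inferred.** SAP 2.5.1 states none, and SAP 2.5 gives only the observed-case basis. With one defined population, all signers is the natural reading but not a stated one. Protocol 10.1 to 10.5 are not visible in the public text, so nothing is concluded from their absence.
4. **The loss is visible and the effect modest.** SAP 2.3.1 tabulates attrition by visit and lists every withdrawal. Crude percentages are a usual descriptive summary, and no comparison between periods is planned.

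Points 1 to 3 narrow the finding and stand. Point 4 limits its weight but does not remove it: a disposition table shows the loss without turning the percentage into an estimate of 48-week incidence.

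**Conclusion.** The concern holds in a conditional form. Crude n/N is the only incidence measure planned, and it makes no allowance for time lost after withdrawal. The extension-period percentage, and the extension part of the whole-period percentage, would be understated if follow-up is incomplete. The pivotal-period table should be essentially unaffected.

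The size is unknown. Under constant hazard and uniform non-informative drop-out it is about 1 percentage point for each 10% of drop-out at an assumed 20% incidence, and zero with complete follow-up. The bias would be larger if hazard rises late, or if subjects leave because of events that go unrecorded. It would be smaller if hazard falls early or if lower-risk subjects leave. A flat statement that incidence is understated is therefore not supported.

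This is an inexpensive improvement to the first component of the safety endpoint, not a flaw that invalidates the analysis.

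**What to change.** In SAP 2.5.1, for the extension period:

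- Keep n/N and the event counts, and state the denominator.
- Add total subject-years of follow-up.
- Add a Kaplan-Meier cumulative incidence of first AE and of first related AE, measured from extension entry and censored at withdrawal or last contact. This allows for non-informative censoring without assuming a constant hazard.
- In the extension-period table only, show the number of subjects with at least one post-entry safety contact beside N.

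Do not remove subjects from the whole-period or pivotal-period denominators. Requiring a post-entry contact there would discard subjects who completed the pivotal study, along with any AEs they had in it.

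The cost is one additional summary to produce and interpret. AE start, visit and withdrawal dates should suffice, with no new data collection. The Kaplan-Meier estimate will be imprecise at about 60 subjects and, like n/N, does not correct for drop-out that is related to AE risk.

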3.1 Safety objective and endpoints

Safety Objective

The objective is to evaluate the long-term safety of Sculptra Aesthetic

Safety endpoint

• Incidence, intensity, time to onset and duration of adverse events (AEs) collected throughout the study period.

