4.4.3 Emergency Unblinding

Not applicable as the Investigator is unblinded.

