6.2 Additional study supplies

No additional study supplies will be provided during this study.

Treatment 6.3

No treatment will be given during this study.

Safety Assessments 7

Assessment of AEs by direct questioning of subject and evaluation of subject

Safety assessments for this study include

It is the responsibility of the Investigator to determine severity of the AE and relatedness of the event to the study product and/or injection procedures. Adverse Events must be reported as outlined below in section 7.2.4.

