7.2 Adverse events

7.2.1 Definition of an adverse event

An AE is any untoward medical occurrence, unintended disease or injury, or untoward clinical signs (including abnormal laboratory findings) in subjects, users or other persons I, whether or not related to the study product.

This definition includes:

- events related to the investigational product or the reference product
- events related to the procedures involved

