1.6 Safety Endpoints

Safety endpoints include incidence, intensity, time to onset, and duration of adverse events collected throughout the study period.

2 Statistical Methods

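### Time to onset and duration belong to the safety endpoint for all adverse events, but SAP 2.5.1 summarises them for related events only

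*SAP*

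**What the plan says.** Protocol 3.1 gives the safety endpoint as "Incidence, intensity, time to onset and duration of adverse events (AEs) collected throughout the study period". SAP 1.6 repeats it: "Safety endpoints include incidence, intensity, time to onset, and duration of adverse events collected throughout the study period". Neither limits the endpoint to events attributed to the product or the injection. Protocol 7.2.1 defines an AE as an untoward occurrence "whether or not related to the study product". SAP 2.5 says that the safety endpoints will be summarised descriptively, without inference.

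SAP 2.5.1 then sets out the tables. All AEs are coded and summarised by SOC and PT, with an overview of subjects and events. Related AEs are broken down by SOC, PT and severity. Onset and duration come next, in a sentence that opens "In addition, for related AEs the number of days to onset from last treatment" and goes on to place the length of the event under the same limit, both by SOC and PT. For the other events the plan is: "Non-related AEs will be summarized by SOC, PT, and intensity". The section ends by asking for these summaries over three periods: the whole period, the 43USSA1705 study alone, and the extension alone.

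Relatedness is decided at the site. Protocol 7.1 states: "It is the responsibility of the Investigator to determine severity of the AE and relatedness of the event".

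**The concern.** The endpoint has four components, and the plan applies a causality filter to two of them that the endpoint definition does not contain. An event judged unrelated is counted and graded, but the planned tables do not say how long after the last injection it began or how long it lasted.

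This matters for the purpose of the study. No treatment is given in the extension, so what it adds to the safety record is later events and their course. Timing and persistence are natural descriptors of such events. For a late event, attribution to an injection in the earlier study is a matter of judgement, and there is no concurrent control group to set it against. With approximately 60 subjects, the classification of one or two events can change what the row for a single PT shows.

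**Working it through.** The documents give no event figure that bears on this, so the check is one of coverage: each endpoint component against each planned summary.

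**Step 1, scope of the endpoint.** Protocol 3.1 and SAP 1.6 carry no qualifier, and the AE definition in Protocol 7.2.1 expressly includes unrelated events. As written, the endpoint covers both classes.

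**Step 2, commitment.** SAP 2.5 promises a descriptive summary of the safety endpoints, without excluding any component or class of event.

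**Step 3, planned tables in SAP 2.5.1.**

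| Component | Related AEs | Non-related AEs |
|---|---|---|
| Incidence | yes | yes |
| Intensity | yes | yes |
| Time to onset | yes | none planned |
| Duration | yes | none planned |

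Four components by two classes give 4 × 2 = 8 cells. A summary is planned for 6, and 8 − 6 = 2 are empty. This counts types of summary, not events.

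**Step 4, is the gap filled elsewhere?**
- The derivation rules in SAP 2.5.1 define onset and duration for an AE in general. They stand beneath the related-AE sentence and add no table for other events.
- The subgroup analyses in SAP 2.5.2 concern related AEs by severity and add neither onset nor duration.
- SAP 2.1.2 promises listings of all eCRF data and derived variables. Recorded AE data will therefore be visible by subject. Whether onset and duration are derived for non-related events is not stated, and a listing is not the summary promised in SAP 2.5.
- Protocol 10.5 (safety analysis) appears in the table of contents, but its text is not in the public version. The mismatch does not depend on it, because it already lies between SAP 1.6 and 2.5 on one side and SAP 2.5.1 on the other.

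**Step 5, would dropping the filter be enough?** Not for duration. Protocol 7.2.6 requires follow-up beyond the last visit only for events causally related to the product or procedure. SAP 2.5.1 calculates duration as stop date minus start date plus 1, and calculates none if the stop date is missing. A non-related event still open at the last visit may therefore never get a duration. A plain all-AE duration table would hold the events that ended under observation and omit the longest ones, so it would understate persistence unless the omitted events are counted beside it.

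**The case against.** The strongest reply is that little information is lost. All AEs appear by SOC and PT, non-related AEs also by intensity, and the tables are repeated for the three periods. That split is itself a coarse display of onset for every AE. A reader might infer that a late cluster called unrelated would vanish from the report. The documents do not support this: the cluster would appear in the extension-period tables, and its events would be in the listings, which are readable at this sample size. This part of the reply stands and limits the point to a missing summary.

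A second reply is that days since the last injection mean little for a plainly intercurrent illness, so a related-only table is a sensible choice. That is fair for onset, less so for duration. If it is the reason, the endpoint should be worded to match.

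Two further inferences also go too far. One is that SAP 2.7 wrongly denies a change from the protocol. SAP 2.7 refers to the statistical methods in the protocol, and since the text of Protocol 10.5 cannot be seen, it may already contain the same limit. The other is that the causality call is suspect because Protocol 4.4.3 says "Not applicable as the Investigator is unblinded". In an open-label follow-up without randomization or blinding, that adds nothing to the plain fact that relatedness is a judgement.

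**Conclusion.** The point holds as an inconsistency within the SAP, shared with Protocol 3.1: time to onset and duration of non-related AEs are part of the stated endpoint and have no planned summary. Its size is 2 of the 8 combinations of component and relatedness. The share of events affected is unknown, because the documents give no relatedness split, and no lost signal can be quantified from them.

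The conclusion assumes that the unqualified endpoint means all AEs, which Protocol 7.2.1 supports, and that the three-period instruction applies to every summary in SAP 2.5.1, which is its natural reading. Safety analysis is descriptive throughout, so no test or interval is affected. This is a worthwhile, inexpensive improvement and not a flaw that undermines the study.

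**What to change.** In SAP 2.5.1, produce the time-to-onset and duration summaries by SOC and PT for all AEs, and keep the related-AE tables as a subset. Beside each duration summary, show the number of events that are ongoing or have no stop date, so that the durations shown are not taken as complete.

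The cost is one extra table set. The existing derivation rules already fit any AE, so no new method is needed. Two limits should be noted with the tables: days from last injection say little about clearly intercurrent events, and observation of non-related events ends at the last visit.

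If the sponsor intends onset and duration for related AEs only, the alternative is to say so in SAP 1.6. That removes the inconsistency at almost no cost, but it narrows the endpoint instead of delivering it as stated.

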1.1.1 Study Design

This is a 48-week prospective, open-label follow-up study, with the aim to evaluate the long-term safety and effectiveness of treatment with Sculptra Aesthetic for correction of Nasolabial Fold (NLF) contour deficiencies. Participation will be limited to the five sites who participated in the 43USSA1705 study.

Eligible subjects in 43USSA1705 were treated with a single regimen of Sculptra Aesthetic [REDACTED]
[REDACTED]
[REDACTED]
[REDACTED]
[REDACTED]

[REDACTED]. Subjects will enter this extension study upon completion of the 43USSA1705 study and perform follow-up visits at [REDACTED] after baseline (i.e. Day1/first treatment session in the 43USSA1705 study).

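### Adverse events with no start date are all dated to day 1 of the extension, so an undated related event from 43USSA1705 is given an onset at or after the end of the study that recorded it

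*SAP*

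**What the plan says.** All the relevant AE rules are in SAP 2.5.1.

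- **Onset:** "Time to onset of an AE will be derived as the start date minus the date of the most recent treatment". It is summarized for related AEs by system organ class and preferred term, using the mean, SD, median and range.
- **Missing start date:** "If the start date is missing, it will be assumed that the AE started on the first day of the extension study".
- **Duration:** "Duration of an AE will be derived as the stop date minus the start date + 1". For missing stop dates: "Missing stop dates will not be imputed and therefore no duration will be calculated in these cases".
- **Periods:** the summaries are produced three times: for both studies combined, for the extension alone, and for 43USSA1705 alone ("The period from baseline to the end of the 43USSA1705 study").
- **Serious events:** "Serious AEs that starts during the extension study will be listed".

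The order of the two studies is fixed in SAP 1.1.1: "Subjects will enter this extension study upon completion of the 43USSA1705 study". Protocol 6.3 states that no treatment is given in the extension, so the most recent treatment is always a 43USSA1705 session. Time to onset is one of the four AE attributes listed as safety endpoints in SAP 1.6 and Protocol 3.1.

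**The concern.** For an event first recorded in the extension the rule is reasonable. Protocol 7.2.3 and 7.2.4 start AE collection at enrollment, so extension day 1 is the earliest onset such an event could have.

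For an event recorded in 43USSA1705 the same date lies at or beyond the latest onset it could have. Two of the three summary periods contain such events, and the public SAP text has no other start-date rule for them. An early related reaction with no start date would therefore be tabulated as a late one. In a study whose purpose is long-term safety, a spurious late-onset related event distorts what the onset table is meant to show. The value would also look plausible, so a range check may not flag it.

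**Working it through.** The plan gives no figure to reproduce, so the check applies its date rules directly.

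**Step 1: the logic, without any assumed date.**

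- Let E be the last day of 43USSA1705 for a subject and X the first day of the extension. SAP 1.1.1 gives X ≥ E.
- An AE recorded in 43USSA1705 began on or before E.
- The rule sets its start to X, so the imputed start is at or after E whatever the true onset was.

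**Step 2: the size of the imputed onset.** Inputs:

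- Extension start: Week 48, inferred from SAP 2.3.4, where a concomitant therapy includes "Any therapy ongoing at the time of V11/Week 48". The period limits in SAP 2.5.1 are blacked out. With baseline as Day 1, Week 48 is 48 × 7 + 1 = Day 337.
- Last session: 0 to 12 weeks after Day 1, that is Day 1 to Day 85. This is an assumption, because the schedule is blacked out.

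Time to onset = imputed start − last treatment:

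- Last session on Day 1: 337 − 1 = 336 days.
- Last session on Day 85: 337 − 85 = 252 days.
- Wider case, last session 24 weeks after Day 1 (Day 169): 337 − 169 = 168 days.

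**Step 3: the effect on one preferred-term row.** Assume one undated event and n − 1 others, all with onset at 5 days. Mean = ((n − 1) × 5 + imputed onset) / n.

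| n | Mean, imputed 252 d | Mean, imputed 336 d | Median | Maximum |
|---|---|---|---|---|
| 5 | (20 + 252)/5 = 54.4 | (20 + 336)/5 = 71.2 | 5 | 252 or 336 |
| 10 | (45 + 252)/10 = 29.7 | (45 + 336)/10 = 38.1 | 5 | 252 or 336 |
| 20 | (95 + 252)/20 = 17.35 | (95 + 336)/20 = 21.55 | 5 | 252 or 336 |

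The undistorted mean in each row would be about 5 days. The median does not move.

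**Step 4: duration, only if the imputed start is also used there.** The SAP neither prescribes nor excludes this. Duration = stop − start + 1:

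- Stop on Day 336: 336 − 337 + 1 = 0 days.
- Stop on Day 300: 300 − 337 + 1 = −36 days.
- Stop on Day 100: 100 − 337 + 1 = −236 days.

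**Step 5: period assignment.** The SAP does not say how an undated event is allocated to a period, and neither option works:

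- If the recording study decides, the 43USSA1705 table contains an onset at or beyond its own end.
- If the imputed date decides, the event can move from the 43USSA1705 table to the extension table and, if serious, into the listing of serious events starting in the extension.

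**The case against.** The strongest reply is that the rule was meant only for extension events. The SAP covers the extension, and day 1 is the natural earliest date for an event newly recorded there. That is probably the intent, but the text does not say it. The section that contains the rule applies its summaries to 43USSA1705 events as well, so the narrow reading leaves those events with no rule in the public text.

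A second reply is that 43USSA1705 dates may already be complete, or completed under that study's own conventions. This may be so and cannot be checked from the two documents. It limits the likely impact but does not correct the wording.

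A third is that data queries (Protocol 9.2.2), independent programming (SAP 2.1.1) and full data listings (SAP 2.1.2) would expose a blank start date beside a long onset. They might. However, programming checks test agreement with the plan, and an output that follows the written rule would agree with it.

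Three points stand. The median resists a single such event. The duration, period and serious-event effects are conditional, because the imputation sentence belongs to the time-to-onset bullet. The sizes above rest on an inferred extension start, an assumed treatment schedule and an invented comparator row.

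**Conclusion.** The rule is wrong as written. That an undated related event from 43USSA1705 is dated to the end of that study or later follows from SAP 1.1.1 and 2.5.1 alone, with no assumed figure and even if the imputed date is used only for time to onset.

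Under the stated assumptions the imputed onset is 252 to 336 days, enough for one event to dominate the mean and maximum of a small preferred-term row. The consequence is a misleading descriptive summary of a named safety endpoint, not a wrong test: SAP 2.5 plans no inferential safety analysis. Whole-period AE incidence is unaffected. The number of affected records is unknown and may be zero. The point should be fixed, but it does not threaten the study.

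**What to change.** In SAP 2.5.1:

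1. Limit the extension-day-1 rule to AEs first recorded in the extension.
2. For AEs recorded in 43USSA1705, apply that study's own missing-date rule if it has one. Otherwise use the earliest date consistent with the known partial, visit and treatment dates, never later than the stop date or the end of 43USSA1705.
3. When the start date is missing, assign the period by the study in which the AE was recorded.
4. Calculate no duration from an imputed start date, in line with the existing treatment of missing stop dates.
5. Footnote the number of imputed start dates in each onset table.

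Items 1 and 2 close the main gap. Items 3 and 4 settle what the SAP leaves open, and item 5 lets the reader judge the effect. The fallback in item 2 is still an imputation and leans toward early onset, which is the reason for showing the count.

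The cost is a few sentences and a small programming change, with no new data. Under SAP 2.1 this is an SAP amendment if made before database lock; after lock it would be documented in the clinical study report.
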